
Aim 3: Two-arm prospective, longitudinal, randomized 18-month intervention with developmental outcomes assessed at 18 months. Recruited caregivers/infants will undergo simple randomization to one of 2 arms. The control arm will receive printed caregiving materials based on recommendations outlined in Table 1. The intervention group will receive the smartphone application. Study staff will make an initial home visit (less than an hour) to install the application on the caregiver phone and demonstrate use. "Teach back" demonstration will be used to assure understanding.

Subsequently, in the intervention arm, staff will make visits every 3 months (less than 1 hour duration) to assess functionality of the smartphone and answer questions/reinforce use.

In the control arm, staff will conduct visits every 3 months (less than 1 hour duration) to ask if there are questions about the printed caregiving materials. The smartphone app in the intervention arm will function as described above in Aim 2, including the semi-structured interview. This intervention phase of the study will last 18 months. The NCAST feeding scale and HOME scale will be administered at visits 0, 6 months, 12 months, and 18 months. The BSID-4 will be measured at 18 months (less than an hour in duration). BSID-4 will be completed during separate assessment visits. There will be a total of 8 home visits by research staff (initial visit, 3 month follow-up visits months 1-6 and 1 visit at the end of the study for BSID-4). Also, during the home visits, research staff will also collect the following information: Infant/caregiver demographics, infant's medical history, caregiver poverty scorecard, and infant's measurements and weight. This information will be collected for research purposes only and will be obtained directly from the caregiver.

Primary Outcome:

The primary outcome is BSID-4 as a measure of infant developmental outcomes. It is a standardized assessment of cognitive, motor, and language development. Research staff interact with the child in a standardized way and observe his or her behavior.

Secondary Outcomes:

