The secondary outcomes are quality of infant-caregiver interaction (NCAST feeding scale) and quality of the home environment (HOME scale). The NCAST is a standardized, reliable assessment of quality of caregiver-infant interaction. Administration consists of videotaping up to 5 minutes of the caregiver feeding the infant. The HOME is a 45-item yes/no checklist completed by an observer to measure the quality and quantity of stimulation and support available to a child in the home environment, which we have validated extensively already in rural Guatemala.

Table 2. Evidence-based guidance for infant care domains to be incorporated into smartphone application.		
Care Domain	Key Guidance	Source
Sleep	
 * Infants sleep around 14-16 hours per day during the first 6 months * Sleep in the supine position * Sleep in the same room as the mother to support responsive breastfeeding 	UNICEF - Guidance on Infant Care at Night
Feeding	
 * Exclusive breastfeeding for first 6 months (following WHO guidelines for acceptable medical reasons for substitute feeding) * Breastfeeding on demand (on average approximately 8-12 times/day) * Avoid additional food or drink other than breastmilk * Sleep in the same room as the mother to support responsive breastfeeding 	WHO - Infant and Young Child Feeding
Activity	
 * Play: "Provide ways for your child to see, hear, feel, move freely, and touch you. Slowly move colourful things for your child to see and reach for. Sample toys: shaker rattle, big ring on a string." * Communication: "Smile and laugh with your child. Talk to your child. Get a conversation going by copying your child's sounds or gestures." 	UNICEF – Care for Child Development

Standard of Care

Aim 1 (Focus Groups) does not involve an intervention. Aims 2 and 3 will compare 2 interventions: printed caregiving materials and a smartphone application. Both interventions will be provided in addition to standard care. All subjects will be recruited from MHA clinics and will continue to be eligible for all standard of care health maintenance services in those settings, regardless of their decision to participate in the study. BSID-4 results will be discussed with the parent or legal guardian and any standard of care recommendations made.

Minimization of Risk

To protect confidentiality, the following steps will be taken:

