For Aim 1, up to 20 caregivers will be recruited in this fashion for formative focus groups. These participants will then be invited, as they are willing, to participate in the formative agile design phase of the app. Subsequently, in Aims 2 and 3, 40 and 220 (respectively) additional caregivers will be recruited in the same fashion into participate in the prospective implementation trial. Given cultural patterns around caregiving in Guatemala, we anticipate that most participants will be female caregivers, but we will make every effort to include male caregivers, including extending joint invitations to both caregivers, making follow-up phone calls to male caregivers when only female caregivers present to clinics, and making research home visits.

The study co-PI ([name]) will monitor recruitment numbers on a biweekly basis, in collaboration with the Maya Health Alliance study team, reporting to the PI [name]. If recruitment numbers are unexpectedly low, the team will consider additional strategies, such as visiting other primary care clinics in town to solicit participation of caregivers referred by other providers and distributing materials announcing the purpose of the study to civic support groups (mothers groups, church groups).

Study retention in rural Guatemala, primarily because of competing demands on time, is at times a concern. For the components of the study requiring longitudinal involvement (Aims 2 and 3), study staff will use three strategies to ensure retention: (1) collect multiple telephone contact numbers, including alternate family member contacts; (2) collect detailed information on location of subject’s home, so that follow-up visits can easily be made to reestablish contact if necessary; (3) develop a formal protocol within the study operating manual, requiring multiple phone calls and at least two attempts at repeat home visits prior to considering a subject lost to follow-up. Taken together, Maya Health Alliance has used these strategies successfully in multiple other projects and are confident they will ensure a high rate of subject retention.

At each study visit, each participant will receive a small care package to compensate for their time. This will contain items commonly provided to participants in other research study and clinical nutrition encounters at Maya Health Alliance (such as high-quality food

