items for family home consumption like eggs and beans, infant diapers and hygiene supplies, infant toys. Care will be taken to avoid toxic items and choking hazards). The approximate value of these items will be US \$5 for each visit.

CONSENT PROCEDURES:

(Explain in detail how, where, when, and by whom consent will be obtained. Describe how coercion in the consent process will be avoided. If research involves children, make certain to fill out the supplementary form on Research involving Children)

After ascertaining initial interest in participation, a research assistant will then make a visit to the primary caregiver at their home (or in another confidential setting, as appropriate) to explain the details of the study, including the nature of the requested involvement in the study, the possible risks and benefits of participation, and the individual capacity to withdraw from the study at any time without consequence. Specific mention will be made of the fact that accessing care from MHA is not conditional on participation in the study, and that there will be no repercussions for declining to participate.

Verbal informed consent will be obtained from all participating caregivers. A verbal consent script will be read to the caregiver, and a copy of the script (in Spanish, as Kaqchikel is mostly an oral language read by very few) will also be provided. Effort will be made to obtain permission from both biological parents or legal guardians if present. However, consent from one parent/guardian will be sufficient to enroll in the trial. Assent will not be sought from enrolled children, as the participating infants (0-18 months of age) are not capable of providing assent.

In addition, given concerns that some caregivers (especially younger women or single mothers) may have restricted agency within their home and might choose to participate but have a family member counteract their decision, we will ask all caregivers if there is another individual who we should discuss the study with to get their permission and, if so, the research assistant will also explain the study to that individual and obtain their assent. In addition, for underage adolescent caregivers (<18 years), assent from the caregiver will be obtained, but consent from the adolescent's legal guardian or parent, since Guatemalan law does not recognize emancipation of minors on the basis of parenthood.

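### In Aim 3, care packages that may contain infant toys go to both arms and can raise toy-related HOME items, which is likely to reduce the sensitivity of this secondary outcome

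*Combined protocol and SAP*

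**What the plan says.** Recruitment Procedures in the Protocol Summary Form states: "At each study visit, each participant will receive a small care package to compensate for their time". The contents are introduced as examples: "items for family home consumption like eggs and beans, infant diapers and hygiene supplies, infant toys". The whole package is worth about US $5 per visit. The text excludes toxic items and choking hazards, but it does not say how many toys are given, of what kind, or how often.

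Under Secondary Outcomes, "The HOME is a 45-item yes/no checklist completed by an observer", and its purpose is "to measure the quality and quantity of stimulation and support available to a child in the home environment". The individual items are not printed. Study Procedures for Aim 3 gives the timing: "The NCAST feeding scale and HOME scale will be administered at visits 0, 6 months, 12 months, and 18 months". The Aim 2 pilot does not use HOME; the summary of aims lists it as an addition in Aim 3.

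The Activity row of Table 2, which sets out the guidance to be built into the app, also names toys: "Sample toys: shaker rattle, big ring on a string".

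The documents do not say whether the baseline HOME is scored before the first package is handed over, or whether toys supplied by the study count when an item is scored.

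**The concern.** The study may place in every home the kind of material that one of its outcome scales is meant to detect and that its guidance encourages. Two things are at stake.

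The first is sensitivity. A yes/no item that a study toy has already satisfied can no longer respond to anything the caregiver does because of the app. Such items then carry less of the contrast between app and print.

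The second is interpretation. A rise in HOME from baseline, in either arm, would mix changes in caregiving with the effect of the gifts. HOME levels in the trial may also not represent homes outside it.

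**Working it through.** **Exposure.** Table 1 gives 8 home visits in Aim 3: an initial visit, visits every 3 months, and one at the end for BSID-4. Reading the three-monthly schedule as months 0, 3, 6, 9, 12, 15 and 18 gives 7 visits, and the BSID-4 visit makes 8. If each package is handed over after that day's HOME, and the BSID-4 visit comes last, the packages received before each HOME are:

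| HOME at month | Earlier packages | Value at $5 each |
|---|---|---|
| 0 | 0 | $0 |
| 6 | 2 | $10 |
| 12 | 4 | $20 |
| 18 | 6 | $30 |

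These are upper limits on the number of packages that held a toy. If the package is handed over before HOME is scored, each count rises by one, and the baseline HOME is affected too.

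**Effect on one item.** Let p_c and p_a be the proportions of control and app homes that pass an item without gifts. Suppose gifts convert a fraction c of failing homes, the same in each arm. Each rate p becomes p + (1 − p)c, so the difference becomes

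(p_a − p_c) − c(p_a − p_c) = (1 − c)(p_a − p_c).

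Example with assumed rates of 40% and 60%, a difference of 20 points:
- c = 0.2: 0.40 + 0.60 × 0.2 = 0.52 and 0.60 + 0.40 × 0.2 = 0.68; the difference is 16 points.
- c = 0.8: 0.40 + 0.60 × 0.8 = 0.88 and 0.60 + 0.40 × 0.8 = 0.92; the difference is 4 points.

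**Effect on the total score.** If the app effect is the same on all 45 items and k of them depend on toys, the share of the HOME difference that is lost is k × c / 45:

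| k (assumed) | c = 25% | c = 50% | c = 100% |
|---|---|---|---|
| 2 | 1.1% | 2.2% | 4.4% |
| 5 | 2.8% | 5.6% | 11.1% |
| 9 | 5.0% | 10.0% | 20.0% |

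For instance, with assumed rates of 50% and 60% on every item, the difference without gifts is 45 × 0.10 = 4.5 points. It becomes 4.45 at k = 2, c = 25% and 3.6 at k = 9, c = 100%.

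If instead a share s of the app effect on HOME lies in the toy-related items, the loss is s × c. With an assumed s of one half, it runs from 0.5 × 0.25 = 12.5% to 0.5 × 1 = 50%.

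**Change within an arm.** With the same 50% and 60%, gifts alone raise the control mean by k × 0.5 × c, from 2 × 0.5 × 0.25 = 0.25 to 9 × 0.5 × 1 = 4.5 points. They raise the app mean by k × 0.4 × c, from 0.2 to 3.6 points. At the upper end, the rise in control homes equals the whole assumed app effect.

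**Power, for scale only.** The protocol calls 110 per arm adequately powered but gives no inputs, so that figure cannot be reproduced. With an assumed two-sided alpha of 0.05, 80% power and no dropout, the detectable standardised difference is (1.960 + 0.842) × √(2/110) = 0.378. If a fraction f of that difference is lost, power is Φ(2.802 × (1 − f) − 1.960):
- f = 10%: 71%; 136 per arm would restore 80%.
- f = 20%: 61%; 172 per arm would restore 80%.

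**The case against.** The case against has several parts, and much of it stands.

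- Toys are one example in a mixed package worth about US $5. A family might receive none. An effect on HOME is therefore possible, not established.
- The HOME items are not in the documents, so both the number of toy-related items and the conversion rate are assumptions. The results must be read as a range.
- An equal additive shift in both arms cancels. This is true of the mean score in general, but it does not describe a yes/no item with equal conversion in the two arms: the homes that can be converted are those failing the item, and the arm doing worse has more of them. For the shift to cancel, gifts would have to convert a larger share of failing homes in the app arm. At 50% and 60% the ratio needed is 0.5 / 0.4 = 1.25. That could happen if toys help app users act on play guidance, and the difference could even widen. Narrowing is the likelier direction, not a certain one.
- Toy guidance may not be exclusive to the app. In Aim 2 the control arm's printed materials are based on Table 2. For Aim 3 the text points to Table 1, which lists the study aims. The contrast may therefore lie mainly in delivery and feedback.
- The protocol says that such items are commonly provided in the organisation's other research and clinical nutrition work, so some may already be part of the background. It also names retention as a concern, which is a reason to keep the package itself.
- The SAP describes an analysis of BSID-4 only, in the past tense, for the six-month pilot. It plans no analysis of change in HOME. The interpretation problem therefore concerns how Aim 3 data may be read, not a test already specified.

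A reader might infer that the gifts bias the trial towards or against the app. The documents do not support this: both arms receive the same package, and the comparison remains a valid one of app against print in the presence of packages. A reader might also infer that BSID-4, the primary outcome of Aim 3, is diluted. That is conceivable, but nothing in the documents allows it to be shown or sized.

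**Conclusion.** The point holds in a limited form. In Aim 3, study-supplied toys can raise toy-related HOME items in both arms. They are likely to reduce the detectable difference on those items, by the factor (1 − c) under equal conversion, and they make change in HOME within an arm hard to interpret. The documents do not support the firmer statement that the trial does shift HOME and narrow the contrast by a known amount.

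For 2 to 9 toy-related items and c of 25% to 100%, the total HOME difference falls by roughly 1% to 20%. This assumes an app effect spread evenly over the 45 items; if the effect is concentrated on play items, the loss is larger. Item counts, conversion rates and the spread of the effect are all assumptions.

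Severity is minor: the point concerns the sensitivity of a secondary outcome, not the validity of the comparison.

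**What to change.** In Aim 3, remove infant toys and any other play or learning item from the care package. Keep the US $5 value with the food, diapers and hygiene supplies already on the list. If a toy is to be given, give it to both arms only after the final HOME and BSID-4.

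This is a one-line protocol change. Visits, staff and package value stay the same, and the only downside is a slightly less varied gift. Aim 2 needs no change on this account because HOME is not measured there.

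If toys are kept, the protocol should state how often they are given, require HOME to be scored before that day's package is handed over, say how study-supplied items are scored, and plan a sensitivity analysis without toy-related items. This is a weaker remedy: scoring before handover protects the baseline but does not remove toys given at earlier visits, and the sensitivity analysis discards part of the scale.

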This was a single-center, individually randomized (1:1 allocation ratio), parallel-group pilot trial to compare use of the smartphone app to printed educational materials. First-time primary caregivers and their infant were eligible to participate if the infant was 0-28 days old at the time of recruitment and a singleton full-term (≥ 37 weeks) birth. Infant exclusion criteria were acute malnutrition (weight-for-length/height Z score ≤ -2 SD using WHO standards), severe medical illness, or medical contraindication to breastfeeding. Caregiver exclusion criteria were inability to read or speak Spanish. Eligible caregivers who did not possess a functioning Android smartphone were given a phone for the duration of the study.

Subjects were recruited by trained research nurses within usual clinical care settings after referral by healthcare providers working at Maya Health Alliance. Verbal consent was obtained following Maya Health Alliance protocol for a minimal-risk study with Indigenous populations as obtaining signatures is not a culturally common practice. Study visits and data collection occurred in the home by trained research nurses, except for the secondary outcome variable (Bayley Scales of Infant Development, Version 4; BSID4; Pearson Assessments, San Antonio, TX, USA) which was collected by consulting psychologists in clinical spaces at Maya Health Alliance.

After enrollment and randomization, caregivers received either the smartphone app, installed with assistance from a study nurse, or printed materials. Brief monthly visits (~ 15 minutes) were conducted monthly for 5 consecutive visits by a study nurse to resolve questions about the app or, in the comparator arm, to resolve any caregiver questions about the printed materials. BSID4 data was collected at enrollment and study exit at 6 months post enrollment.

STATISTICAL ANALYSIS PLAN

Quantitative statistical analysis was conducted using Stata Version 17. Demographic and clinical characteristics of study participants were summarized using means and standard deviations; median and interquartile range; or percentages, as appropriate. For BSID4 outcomes, raw differences between intervention and control arms in composite scores were summarized and adjusted differences calculated using linear regression with adjustments chosen *a priori* for sex of child, caregiver educational level, poverty score, birth weight and change in length for age Z score from 0 to 6 months.
